3.1.2 Physician Population and Eligibility

This cross-sectional study will be conducted in each of the five countries (the UK, Germany, France, Italy, and Spain) with distribution among a variety of physician specialties including, for example, general practitioners, cardiologists (office and hospital), haematologists, hospital stroke physicians, emergency care physicians, phlebologists, neurologists, angiologists, and other specialists in internal medicine (office and hospital). Representation by each physician group will reflect, to the extent possible, prescribing patterns in each country. Physicians will complete an online questionnaire eliciting information about their knowledge and use of the prescriber guide for rivaroxaban.

Physicians will be eligible to participate in this study provided they have prescribed rivaroxaban to at least one patient in the past 6 months for one of the following indications:

- Prevention of stroke and systemic embolism in adult patients with non-valvular atrial fibrillation (SPAF).
- Treatment of DVT and prevention of recurrent DVT and PE following an acute DVT in adults.

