3.1.3 Physician Selection and Recruitment

The physician sampling frame will be constructed from a physician panel and/or prescriber list. The final frame will be determined with the objective of achieving a generally representative sample of physicians prescribing rivaroxaban. Geographic location, speciality, practice size, practice type, etc. will be taken into consideration. If the distribution of

physicians in the sampling frame appears consistent with the distribution believed in the targeted population, physicians will be randomly selected from the sample frame. However, if the distributions do not appear consistent with the targeted population, the sampling frame will be stratified by speciality and/or geography, and specific numbers of physicians within each stratum will be selected in order to recruit a sample that matches the distribution in the target population. In this case, the physician recruitment within each stratum will be done randomly. The final sampling strategy will be determined once rivaroxaban is on the market and will be designed to minimise bias and to allow for the study results to be generalised to the entire population of rivaroxaban prescribers to the extent feasible.

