3.1.6 Physician Data Collection

A Web-based electronic data capture (EDC) system will be used in this study. An invitation will be sent to the selected sample of physicians, inviting them to participate and providing a link to the Web-based questionnaire. During the data collection period, invitations will be made via e-mail or issued by phone to each sampled physician up to two times. Each invited physician will be asked to log in to the study Web site by entering a unique identification number and password assigned to each participant and provided in the invitation to participate. The questionnaire will begin with informed consent. After participants consent, they will be prompted to complete the questionnaire. A screening question will be included at the beginning of the questionnaire to confirm that the physician has prescribed

rivaroxaban at least once within the past 6 months for at least one of the two new indications.

The questionnaire will be self-administered (closed-ended questions with predefined answers) and can be completed at the participants' convenience. Although participants will be encouraged to complete the questionnaire in a timely manner, once they start the questionnaire, they will be able to stop at any point and, at a later time, pick up where they left off, should that be necessary. Participants will not be able to go back and change answers to previous questions. This restriction minimizes the likelihood of the respondent searching for answers via the Web or other sources.

Participants will also not be allowed to access the questionnaire once it has been completed. Based on potential country-specific requirements, the recruitment process and physician questionnaire may be different between countries. Country-specific differences will be described and appended to the final study protocol.

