3.5.5 Compensation

Physician sites participating in the patient assessment will be paid nominal incentives to compensate them for the time spent recruiting patients and providing limited data from patient records, per country-specific regulations. The amount and payment methods will be reviewed and approved by the IRB/EC to ensure that payments are commensurate with the time needed to complete the study tasks and are not coercive.

Patients and physicians participating in the assessments will be paid nominal incentives to compensate them for their time in completing the study questionnaires in those countries where it is acceptable to do so. As with the site compensation, the amount and payment methods will be reviewed and approved by the IRB/EC to ensure that payments are commensurate with the time needed to complete the forms, not coercive, and made according to local regulations in each country.

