Appendix C.

Physician Questionnaire

To confirm your eligibility to participate in this brief assessment, please answer the following question:

S1. In the past 6 months, have you prescribed Xarelto (rivaroxaban) to patients for either of the following indications?

(Tick all that apply.)

- Prevention of stroke and systemic embolism in adult patients with non-valvular atrial fibrillation
- Deep vein thrombosis treatment and secondary prevention in adults
- I have not prescribed Xarelto for either of these indications

[IF S1 = “I have not prescribed Xarelto for either of these indications”, THEN DISPLAY “It does not appear that you qualify for the survey. Thank you for your time and interest.” AND TERMINATE SURVEY ELSE DISPLAY “We have confirmed that you are eligible. We will now continue with the survey questions].

Physician Questionnaire

This questionnaire is designed to gain a better understanding of prescribers’ knowledge about Xarelto for only the following two approved indications:

- Prevention of stroke and systemic embolism in adult patients with non-valvular atrial fibrillation
- Deep vein thrombosis treatment and secondary prevention

Additionally, this assessment will be used to determine if the education materials regarding Xarelto, including the Prescriber Guide, are accurately understood and whether there are aspects of these materials that could be improved.

The first set of questions asks about your prescribing practices.

Q1. In the past 6 months, for how many patients have you prescribed Xarelto for the prevention of stroke and systemic embolism in patients with non-valvular atrial fibrillation?

- 1 to 10
- 11 to 20
- 21 or more
- I have not prescribed Xarelto for this indication

Q2. In the past 6 months, for how many patients have you prescribed Xarelto for deep vein thrombosis treatment and secondary prevention?

- 1 to 10
- 11 to 20
- 21 or more
- I have not prescribed Xarelto for this indication

Q3. When did you write your most recent prescription for Xarelto for either of these indications?

(Tick one.)

- Less than 1 month ago
- 1 to 3 months ago
- 4 to 6 months ago
- I don't know

Q4. Which of the following Xarelto treatment activities are you responsible for?

(Tick all that apply.)

- I initiate Xarelto treatment or convert treatment from or to Xarelto
- I write follow up (maintenance) prescriptions for Xarelto

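### Physician eligibility rests on a transparent self-report screener, and respondents who later deny prescribing for both indications stay in the survey

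*Protocol*

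**What the plan says.** Section 3.1.2 admits physicians "provided they have prescribed rivaroxaban to at least one patient in the past 6 months for one of the following indications". Section 3.1.6 says how this is established: "A screening question will be included at the beginning of the questionnaire to confirm that the physician has prescribed" the drug within that window. No record check is described.

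Appendix C prints the question. The lead-in is "To confirm your eligibility to participate in this brief assessment, please answer the following question", and S1 then asks "In the past 6 months, have you prescribed Xarelto (rivaroxaban) to patients for either of the following indications". The options are the two study indications and "I have not prescribed Xarelto for either of these indications". That last option ends the survey; otherwise the screen shows "We have confirmed that you are eligible. We will now continue with the survey questions". No other drug or indication is listed.

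Q1 and Q2 then ask for patient numbers under each indication, and each allows the physician to say that none were treated. In the printed routing, that answer at Q1 skips Q16-Q17 and at Q2 skips Q18. Neither answer, nor both together, ends the survey.

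Two further sections bear on exposure. Section 3.1.3 states: "The physician sampling frame will be constructed from a physician panel and/or prescriber list". Section 3.5.5 states: "Patients and physicians participating in the assessments will be paid nominal incentives", limited to countries that permit payment and subject to ethics review of the amount.

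**The concern.** The qualifying answer to S1 can be read off the screen. A panel member who does not prescribe the drug but wants to take part, or is offered payment, knows what to tick. Q1 and Q2 could expose such a respondent, but the printed instrument does nothing with the contradiction. Someone who denies both indications still answers Q5-Q15 (knowledge) and the items from Q19 on (receipt and use of the materials).

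The target quantities in Section 2 are receipt, knowledge and use among prescribers. A physician who does not prescribe the drug has less reason to have received the guide or the alert cards, or to know their content, so the likely direction of bias is downward. A larger sample does not reduce this bias. The limitations in Section 5 cover non-response and Internet access, but not false qualification.

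**Working it through.** **Inputs from the protocol.** 300 physicians per country and about 1,500 overall (Section 3.1.4); exact 95% limits at 85% correct of 80.4% to 88.8% for n=300 and 83.1% to 86.8% for n=1,500 (Table 1).

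**Inputs assumed, because the protocol gives none.** Share of non-prescribers among respondents, c = 2% to 15%; their percentage correct, q = 50% to 60%, against p = 85% in true prescribers.

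**Step 1: the protocol's own precision.** Clopper-Pearson limits reproduce all eight rows of Table 1. Half-width at n=300: (88.8 − 80.4)/2 = 4.2 points. At n=1,500 the unrounded half-width is 1.84 points. For the 1,200 physicians at 18 months the same method gives 82.9% to 87.0%, about 2.1 points.

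**Step 2: bias in knowledge.** Observed = (1 − c)·p + c·q, so bias = c·(q − p).

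| c | q = 60% | q = 50% |
|---|---|---|
| 2% | 0.02 × (−25) = −0.5 | 0.02 × (−35) = −0.7 |
| 5% | −1.25 | −1.75 |
| 10% | −2.5 | −3.5 |
| 15% | −3.75 | −5.25 |

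The bias equals the pooled half-width at c = 1.84/35 = 5.3% (q = 50%) or 1.84/25 = 7.4% (q = 60%). It equals the single-country half-width at 4.2/35 = 12.0% or 4.2/25 = 16.8%. With a wider q at c = 10%, the bias is −1.5 points for q = 70% and −5.2 points for q = 33%.

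**Step 3: bias in receipt.** Assume 70% receipt in prescribers and 0% to 40% in non-prescribers. At c = 10%, observed receipt is 0.9 × 70 + 0.1 × 0 = 63% to 0.9 × 70 + 0.1 × 40 = 67%, a fall of 3 to 7 points.

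**Step 4: how c depends on the frame.** Let π be the prescriber share among those who reach S1 and f the share of non-prescribers who pass it, with all prescribers passing. Then c = (1 − π)f / [(1 − π)f + π].

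- π = 90%, f = 10% to 30%: 0.01/0.91 = 1.1% to 0.03/0.93 = 3.2%.
- π = 70%, f = 10% to 30%: 0.03/0.73 = 4.1% to 0.09/0.79 = 11.4%.

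A frame close to a true prescriber list makes the problem small; a mixed panel can make it matter for the pooled estimate.

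**The case against.** S1 asks exactly what Section 3.1.2 requires and terminates correctly, so the protocol does not contradict itself. Access is by individual invitation with a unique identifier and password, and answers cannot be changed, which limits repeated attempts. Q1-Q4 ask about patient numbers, the date of the last prescription and prescribing role, and Section 3.6 promises edit and logic checks. Those checks could catch an S1 conflict, and the detailed rule may sit in a data management or analysis plan. All of this stands, but none of it hides the qualifying answer, and the questionnaire, which Section 3.1.5 calls final, fixes routing that keeps a self-declared non-prescriber in.

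A reader might infer that the sample will be paid members of a general panel and that results will be distorted. The documents do not support that. A prescriber list is an equally permitted frame and would itself be evidence of prescribing. Payment is nominal and depends on the country. Section 5 speaks only of a possible delay in uptake, and raises it as a threat to representativeness; it does not predict false qualification.

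The remedy also has limits. Consent comes before S1, so a list of decoys hides little if consent names the product. The instrument has been cognitively tested with 25 physicians, so a new item is not free.

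**Conclusion.** The point holds as a modest design weakness. Eligibility is confirmed only by self-report, the screener shows which answer qualifies, and denial at both Q1 and Q2 has no consequence beyond skipping Q16-Q18. Where the frame is a panel and physicians are paid, some non-prescribers could enter and bias the estimates.

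The size is unknown. Under the assumed 2-15% contamination and 50-60% correct against 85%, the knowledge bias is about 0.5 to 5 points. The low end is negligible beside either half-width. The high end exceeds the 4.2 points for a country sample, and the pooled 1.8 points is passed at roughly 5% to 7% contamination. The downward direction is plausible but not established: if non-prescribers answered as well as prescribers, the knowledge bias would vanish. This is an inexpensive improvement and does not invalidate the physician assessment.

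**What to change.** 1. Replace the eligibility sentence above S1 with a neutral lead-in about prescribing practice.
2. Ask S1 as a list of several anticoagulants and indications prescribed in the past six months, plus a none option, without showing which combination qualifies. Qualify on Xarelto for either study indication.
3. Terminate, or exclude from analysis, any respondent who answers at both Q1 and Q2 that they have not prescribed for that indication. This needs no new question wording and could be adopted even if S1 stays as printed, though it catches only those who contradict themselves.

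Cost: about 30 seconds more per physician, Web reprogramming, translation of one item and possibly an ethics notification. Sample size and confidence-interval method are unchanged. Masking will be only partial where the invitation or consent names the product.

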1 BACKGROUND

Xarelto[®] (rivaroxaban) is a highly selective direct Factor Xa inhibitor with oral bioavailability. Inhibition of Factor Xa interrupts the intrinsic and extrinsic pathway of the blood coagulation cascade, inhibiting both thrombin formation and development of thrombi. Rivaroxaban does not inhibit thrombin (activated Factor II), and no effects on platelets have been demonstrated. It does not require routine coagulation monitoring and has no food interactions and only a few drug interactions compared to standard of care (Xarelto Summary of Product Characteristics—EU, 2011).

Rivaroxaban is currently indicated for the prevention of venous thromboembolism in adult patients undergoing elective hip or knee replacement surgery. Rivaroxaban has recently received a positive opinion by the European Committee for Medicinal Products for Human Use (CHMP) for the prevention of stroke and systemic embolism in adult patients with non-valvular atrial fibrillation (AF) and treatment of deep vein thrombosis (DVT), and for prevention of recurrent DVT and pulmonary embolism (PE) following an acute DVT in adults (Xarelto Summary of Product Characteristics—EU, 2011.)

Atrial fibrillation is the most common cardiac arrhythmia of clinical significance and is an important independent risk factor for cardiogenic thromboembolic events. The prevalence of AF increases with age, being less than 1% among people under 60 years of age, with estimates of more than 6% among those over 80 years of age (Feinberg et al., 1995). AF is estimated to affect over 6 million patients in Europe and approximately 2.3 million in the United States (US), and the number of patients with AF continues to grow in the ageing population (Kannel and Benjamin, 2008). AF is associated with a four- to five-fold increased risk of ischemic stroke (Wolf et al., 1991) and accounts for up to 15% of all strokes and 30% of strokes in patients over the age of 80 (Wolf et al., 1987). In addition, there is evidence that AF-associated stroke is more disabling than non-AF-associated stroke (Jorgensen et al., 1996).

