3.1.5 Physician Questionnaire Development

Standard survey methodologic principles have been used to develop the physician questionnaire, which will assess physicians' knowledge of the following concepts as outlined in the prescriber guide and educational materials:

- Switching from or to rivaroxaban treatment
- Necessity of taking the 15-mg and 20-mg tablets with food
- Use of coagulation tests and their interpretation
- Dosing recommendations
- Perioperative management
- Populations at higher risk of bleeding
- Necessity of providing all patients with a patient alert card and counselling about the details of the patient alert card

Physicians will be asked about their receipt and use of the prescriber guide (Appendix A) as well as counselling of patients and distribution of the patient alert card. In addition, physicians will be asked to characterise their practice in terms of years in practice, size of practice, and history of treating patients with the diagnoses of interest. Other characteristics will be collected to facilitate stratified analyses to explore factors associated with knowledge and behaviour. The physician questionnaire is designed to take 10-15 minutes to complete. The physician questionnaire has been cognitively tested with physicians in each of the target countries. Section 3.3 provides a detailed description of the cognitive pretesting process. Modifications have been made to the questionnaire based on the pretesting results and additional feedback from the sponsor. The final version of the questionnaire can be found in Appendix C. Some modifications to the questionnaire are anticipated based on country-specific requirements.

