Xarelto 15mg and 20mg must be taken with food to ensure sufficient absorption of the drug. The intake of these doses with food at the same time supports the required absorption of the drug, thus ensuring a high oral bioavailability.

Note: Xarelto is also available at a 10mg dose for the prevention of venous thromboembolism (VTE) in adult patients undergoing elective hip or knee replacement surgery. This dose can be taken with or without food.

Dosing in patients with AF

The recommended dose for prevention of stroke and systemic embolism in patients with non-valvular AF is 20mg once daily.

*In patients with moderate or severe renal impairment the recommended dose is 15mg once daily.

Patients with renal impairment:

In patients with moderate (creatinine clearance 30-49 ml/min) or severe (15-29 ml/min) renal impairment the recommended dose is 15mg once daily. Xarelto is to be used with caution in patients with severe renal impairment as limited clinical data indicates a significantly increased plasma concentration. Use is not recommended in patients with creatinine clearance $<$ 15 ml/min.

Duration of therapy:

Xarelto should be continued long term provided the benefit of stroke prevention therapy outweighs the potential risk of bleeding. Clinical surveillance in line with anticoagulation practice is recommended throughout the treatment period.

[figure not shown]

Missed dose:

If a dose is missed the patient should take Xarelto immediately and continue on the following day with the once daily intake as recommended. The dose should not be doubled within the same day to make up for a missed dose.

Dosing in treatment of DVT and PE, and prevention of recurrent DVT and PE in adults

Patients are initially treated with 15mg **twice daily** for the first three weeks. This initial treatment is followed by 20mg **once daily** for the continued treatment period.

* Patients with DVT/PE and renal impairment

Patients with renal impairment

Patients with moderate (creatinine clearance 30-49 ml/min) or severe (15-29 ml/min) renal impairment treated for acute DVT, acute PE and prevention of recurrent DVT and PE do not require a dose reduction.

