Presentation: 10 mg rivaroxaban tablet. **Indication(s):** Prevention of venous thromboembolism (VTE) in adult patients undergoing elective hip or knee replacement surgery. **Posology and method of administration:** Dosage 10 mg rivaroxaban orally once daily with or without food; initial dose should be taken 6 to 10 hours after surgery provided haemostasis established. **Recommended treatment duration:** Dependent on individual risk of patient for VTE determined by type of orthopaedic surgery: for major hip surgery 5 weeks; for major knee surgery 2 weeks. Refer to SmPC for full information on duration of therapy & converting to/from Vitamin K antagonists (VKA) or parenteral anticoagulants. **Renal impairment:** Mild & moderate (creatinine clearance 50-80ml/min & 30-49 ml/min respectively) – no dose adjustment necessary; severe (creatinine clearance 15-29ml/min) – limited data indicates rivaroxaban concentrations are significantly increased, use with caution. Patients with creatinine clearance < 15ml/min – use not recommended. **Hepatic impairment:** Do not use in patients with hepatic disease associated with coagulopathy & clinically relevant bleeding risk including cirrhotic patients with Child Pugh B & C patients. **Paediatrics:** Not recommended. **Contra-indications:** Hypersensitivity to active substance or any excipient; clinically significant active bleeding; hepatic disease associated with coagulopathy and clinically relevant bleeding risk including cirrhotic patients with Child Pugh B & C; pregnancy & breast feeding. **Warnings and precautions:** Not recommended in patients: undergoing hip fracture surgery; in patients receiving concomitant systemic treatment with strong CYP3A4 and P-gp inhibitors, i.e. azole-antimycotics or HIV protease inhibitors; with severe renal impairment (creatinine clearance <15 ml/min). Increased risk of bleeding therefore careful monitoring for signs/symptoms of bleeding complications & anaemia required after treatment initiation: in patients with severe renal impairment (creatinine clearance 15 - 29 ml/min); or with moderate renal impairment (creatinine clearance 30 - 49 ml/min) concomitantly receiving other medicinal products which increase rivaroxaban plasma concentrations; in patients treated concomitantly with medicinal products affecting haemostasis; in patients with congenital or acquired bleeding disorders; uncontrolled severe arterial hypertension; active ulcerative gastrointestinal disease (consider appropriate prophylactic treatment for at risk patients); recent gastrointestinal ulcerations; vascular retinopathy; recent intracranial or intracerebral haemorrhage; intraspinal or intracerebral vascular abnormalities; recent brain, spinal or ophthalmological surgery, bronchiectasis or history of pulmonary bleeding. There is no need for monitoring of coagulation parameters during treatment with rivaroxaban in clinical routine. If clinically indicated rivaroxaban levels

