The next questions ask about the use of Xarelto for prevention of stroke and systemic embolism in patients with non-valvular atrial fibrillation and deep vein thrombosis treatment and secondary prevention.

Q5. What is the most important risk associated with taking Xarelto?

(Tick one.)

- Neoplasia
- Hypertension
- Risk of bleeding
- Immunosuppression
- I don't know

Q6. Which of the following populations are at an increased risk of experiencing serious side effect(s) associated with Xarelto?

(Tick Yes, No, or I don't know for each patient population listed)

| Population | Yes, at higher risk | No, not at higher risk | I don't know |
|--|--------------------------|---------------------------|--------------------------|
| Patients with moderate or severe renal |  |  |  |

| | | | |
|---|--------------------------|--------------------------|--------------------------|
| impairment | | | |
| Patients taking products that affect hemostasis such as NSAIDS, acetylsalicylic acid, platelet aggregation inhibitors |  |  |  |
| Patients at risk of bleeding |  |  |  |
| Patients with chronic constipation |  |  |  |

Q7. To which patient groups is Xarelto contraindicated?**(Tick all that apply.)**

- Patients with hepatic disease associated with coagulopathy and clinically relevant bleeding risk including cirrhotic patients with Child Pugh class B and C
- Patients who are pregnant or breastfeeding
- Patients receiving concomitant treatment with any other anticoagulant such as unfractionated heparin (UFH), low molecular weight heparins, heparin derivatives or oral anticoagulants except when switching therapy to or from Xarelto or when UFH is given at doses necessary to maintain a patent central venous or arterial catheter
- Patients with clinically significant active bleeding
- I don't know

Q8. Xarelto (15 or 20 mg) must be taken....?**(Tick one.)**

- On an empty stomach
- With food/on a full stomach
- I don't know

Q9. Is routine coagulation monitoring required for patients taking Xarelto for these indications?

- Yes
- No
- I don't know

Q10. In which of the following situations is INR monitoring needed?**(Tick all that apply.)**

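### Physician Q8 has no option for a respondent who believes food is irrelevant, so the percentage correct on the food message is liable to be overstated

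*Protocol*

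**What the plan says.** Section 3.1.5 of the protocol lists, among the concepts the physician questionnaire must assess, "Necessity of taking the 15-mg and 20-mg tablets with food". The prescriber guide in Appendix A (Dosing recommendations) gives the message itself: "Xarelto 15mg and 20mg must be taken with food to ensure sufficient absorption of the drug". A note directly below it describes the 10 mg tablet differently: "This dose can be taken with or without food". The 10 mg prescribing information in the same appendix repeats this: "10 mg rivaroxaban orally once daily with or without food".

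Appendix C tests the message once, in Q8. The stem is "Xarelto (15 or 20 mg) must be taken", one tick is allowed, and the options are "On an empty stomach", "With food/on a full stomach" and *I don't know*. Section 3.1.5 describes Appendix C as the final questionnaire, while expecting some country-specific changes. No answer key is printed. The keyed answer is taken here from the guide text.

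**The concern.** The guide contrasts a strength that needs food with a strength for which food does not matter. Q8 instead contrasts a full stomach with an empty one. Nothing in the guide or the alert card suggests an empty stomach, so the only substantive wrong answer is a weak one.

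The missing belief is a plausible one for prescribers. Section 1 records that the drug was first used in another setting: "Rivaroxaban is currently indicated for the prevention of venous thromboembolism in adult patients undergoing elective hip or knee replacement surgery". Appendix A identifies that as the 10 mg indication. Section 1 also describes the drug as free of food interactions.

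The primary objective is to measure understanding of the key messages. If some physicians who think food is irrelevant are counted as knowing the rule, Q8 reports better understanding than exists. It also cannot show which misunderstanding the materials would need to correct. Section 1 plans assessments at 18 months, 3 years and 7 years, so an unchanged item repeats the problem each time.

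**Working it through.** **1. Can the belief be expressed?** Compare items in which a respondent might want to deny a requirement.

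| Item | Subject | Option denying the requirement |
|---|---|---|
| Physician Q9 | Routine coagulation monitoring | Yes (*No*) |
| Physician Q14 | Stopping before a procedure | Yes (stopping is unnecessary) |
| Patient Q14 (first questionnaire) | Food with 15 mg and 20 mg | Yes (*No*) |
| Physician Q8 | Food with 15 mg and 20 mg | None |

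Physician Q16, Q17 and Q18 each include a 10 mg once-daily regimen among the wrong answers, so the questionnaire already allows for confusion with that strength. Q8 does not offer the corresponding food rule.

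**2. The protocol's precision figure.** Section 3.1.4 and Table 1 give an exact 95% interval of 80.4% to 88.8% for 85% correct among 300 physicians. The Clopper-Pearson interval for 255/300 (0.85 × 300 = 255) reproduces this. The lower arm is 85.0 − 80.4 = 4.6 points. For 1,500 physicians, Table 1 gives 83.1% to 86.8%, a lower arm of 85.0 − 83.1 = 1.9 points.

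**3. Size of the overstatement.** Let m be the share of physicians who believe food is irrelevant, and w the share of those who tick the keyed answer because their own is absent. Assume that physicians who know the rule tick the keyed answer. Then

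observed correct = true knowledge + m × w, so bias = m × w ≥ 0.

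The documents give neither m nor w. The ranges below are assumptions. For an observed 85%, true knowledge would be:

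| m | w = 0 | w = 0.5 | w = 1 |
|---|---|---|---|
| 5% | 85.0% | 82.5% | 80.0% |
| 10% | 85.0% | 80.0% | 75.0% |
| 20% | 85.0% | 75.0% | 65.0% |

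The bias runs from 0 points (w = 0) to 20 points (m = 20%, w = 1).

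**4. When does it exceed the sampling error?** At 300 physicians, m × w must exceed 4.6 points:

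- m = 5%: w above 4.6/5 = 0.92
- m = 10%: w above 4.6/10 = 0.46
- m = 20%: w above 4.6/20 = 0.23

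With m = 5% and w = 0.5 the bias is 2.5 points, inside the arm at 300 physicians but outside the 1.9-point arm at 1,500. A larger sample narrows the interval and leaves the bias unchanged.

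**The case against.** The strongest case against is that the documents hold no data on what physicians believe about food, so the importance of the missing option is a judgement. Several features also soften the problem. The stem names the two strengths, and the introduction limits the survey to the two indications, which reduces any cue towards the 10 mg rule. *I don't know* is available. Section 3.3 reports cognitive pretesting with 25 physicians in five countries, aimed partly at response choices. The analysis is descriptive, no pass mark is set, and one item among many is affected.

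Most of this stands, and it limits how far the point can be pushed. A reader might infer three stronger things that the documents do not support:

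- **That the guide warns against carrying the 10 mg rule over.** It contains only a neutral note on the 10 mg tablet. The dose distractors in Q16 to Q18 show that confusion over dose was anticipated, which is not the same as confusion over food.
- **That Q8 scores every physician who thinks food is irrelevant as correct.** Only those who tick the keyed answer are. The others may choose the empty-stomach option or *I don't know*.
- **That the bias exceeds the stated precision.** That depends on two unknown shares and fails for part of their range.

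The mitigating features do not remove the gap. A firm but wrong belief is not a *don't know*. Pretesting with an average of five physicians per country (25/5) may well not reveal an absent answer.

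**Conclusion.** The point holds as a defect of item design. Q8 is the sole physician measure of a listed key message, and it does not let a respondent state that food is irrelevant. The percentage correct is therefore liable to be overstated. The direction is known (upward or zero). The size is not: 0 to 20 points under the assumed ranges of 5% to 20% for the belief and 0 to 1 for the share ticking the keyed answer. The overstatement matters relative to the sampling error at 300 physicians and 85% correct only if the product of those shares is about 5 points or more. No statistical analysis plan can recover an answer that was never offered, so a remedy at source is worthwhile. A caveat in the report would disclose the limitation without measuring it.

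**What to change.** Before fielding, replace the stem with a neutral one, for example: *How should Xarelto 15 mg and 20 mg tablets be taken in relation to food?* Add the option *With or without food*, keep the three existing options, and score against the guide text. This changes only the measurement and leaves the dosing message as it is.

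The cost is one edit to a Web form, translation for each country, a brief check of the new wording (the completed pretesting did not cover it), and any notification required under the ethics approvals in Section 3.5.1. The percentage correct may come out lower. Making the change before the first assessment also keeps the item identical across the three time points. A later change would break comparability on this item.
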